#### 3.2.3.1.3 *Alternative assumption of missing data (tipping-point analysis) (for Definition 1 and Definition 2 respectively)*

The tipping point analyses will be two-dimensional, i.e., assumptions about the missing outcomes in each treatment group would vary independently. The response rate among those participants with missing durable response status (identified in [Table 5](#)) is assumed to be  $p_0$  for the placebo group and  $p_1$  for the rilzabrutinib group, and the response rate  $p_0$  and  $p_1$  will systematically vary starting from 0% and ending at 100% by every 10% respectively. Given a set of  $(p_0, p_1)$ , a participant with missing response will be randomly assigned as a responder or a non-responder using binomial distribution to generate multiple imputed datasets. The same analysis method as defined in the main analytical approach ([Section 3.2.2](#)) will be performed on each of the imputed datasets to obtain the results for each comparison of the rilzabrutinib group versus the placebo group. The results across multiple imputed datasets will be combined using Rubin's rule ([3](#)). If one pair of  $(p_0, p_1)$  is found to just reverse the study conclusion, in terms of p-value larger than 0.05, then the  $(p_0, p_1)$  is identified as the tipping point. The results for a grid of  $(p_0, p_1)$  combinations will be provided.

Please see sample SAS® code in [Section 5.7](#).

**Table 5 - Tipping Point Analysis: Durable Platelet Response Status**

Definition	Criteria (during the last 12 weeks of DB on-treatment period)	Status
Definition 1 a	Rescued after 8 weeks of treatment and before Week 25	Non-responder
	Discontinued before Week 25 due to related TEAE or lack of response	Non-responder
	Observed non-responder: $\geq 5$ weekly platelet counts $< 50,000/\mu\text{L}$	Non-responder
	Observed responder:	Responder
	1. $\geq 8$ weekly platelet counts $\geq 50,000/\mu\text{L}$ , OR 2. 6 or 7 weekly platelet counts $\geq 50,000/\mu\text{L}$ in total out of $\geq 8$ non-missing weekly platelet counts among which $\geq 2$ weekly platelet counts $\geq 50,000/\mu\text{L}$ out of last 6 weeks	
	Undetermined: due to missing data, or discontinuation not due to related AE or lack of response	Missing
Definition 2 b	Rescued after 8 weeks of treatment and before Week 25	Non-responder
	Discontinued before Week 25 due to related TEAE or lack of response	Non-responder
	Observed non-responder: $\geq 5$ weekly platelet counts $< 50,000/\mu\text{L}$	Non-responder
	Observed responder: $\geq 8$ weekly platelet counts $\geq 50,000/\mu\text{L}$	Responder
	Undetermined: due to missing data, or discontinuation not due to related AE or lack of response	Missing

a Definition 1. Durable platelet response defined as a proportion of participants able to achieve platelet counts at or above  $50,000/\mu\text{L}$  for  $\geq$  two-thirds of at least 8 non-missing weekly scheduled platelet measurements during the last 12 weeks of the 24-week blinded treatment period in the absence of rescue therapy, provided that at least 2 non-missing weekly scheduled platelet measurements are at or above  $50,000/\mu\text{L}$  during the last 6 weeks of the 24-week blinded treatment period. Definition 1 not applicable to countries within the EU (EEA countries) and UK.

b Definition 2. Durable platelet response defined as a proportion of participants able to achieve platelet counts at or above  $50,000/\mu\text{L}$  for at least 8 out of the last 12 weeks of the 24-week blinded treatment period in the absence of rescue therapy. Definition 2 applicable to countries within the EU (EEA countries) and UK only.

TEAE = treatment emergent adverse event.

### 3.2.3.2 Sensitivity Analyses – modified primary estimand – Adults in mITT, 24-week completer, participants not receiving Covid-19 vaccine (for Definition 1 and Definition 2, respectively)

Sensitivity analyses in adults will be performed to assess respectively, the potential impact of,

- Non-IMP exposure by including participants who have been randomized and exposed (ie, mITT)
- The premature discontinuation by including participants who have completed the 24-week double-blind treatment period without rescue medication (ie, 24-week completer).
- The Covid-19 vaccine by including participants who did not receive Covid-19 vaccine during the last 16 weeks of the double-blind treatment period.

Each sensitivity analysis will be carried out via a modified primary estimand, which is the same as the primary estimand defined in the main analytic approach, except for the analysis population. The same analysis as specified in [Section 3.2.2](#) will be performed ([Table 4](#)).

For the analysis in the 24-week completer, the treatment difference will likely be estimated via normal approximation without being adjusted by stratification factors due to the expected high dropout particularly in the placebo group. The analysis method and stratification factors will be specified in the footnote of the corresponding outputs.

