4. STUDY DESIGN

This is a global, randomized, parallel-group, double-blind, multicenter clinical study in patients with primary ITP who had a response to either IVIg or CS that was not sustained.

After providing informed consent, participants will enter a 28-day screening period. Upon completion of the screening period, participants who satisfy all the inclusion criteria and none of the exclusion criteria of this protocol will be randomized in a 2:1 allocation ratio to one of two study arms: rilzabrutinib or placebo. Randomization will be carried out separately for the two age groups. For the adult group, stratified permuted block randomization will be implemented; for the pediatric group, dynamic randomization algorithm (minimization) will be implemented. The factors used for stratification (for adult participants), or balance (for pediatric participants) are splenectomy status (yes/no), and by severity of thrombocytopenia (Inclusion Criteria #3 platelet counts $<15,000/\mu\text{L}$ or $\geq 15,000/\mu\text{L}$).

[figure not shown]
After randomization, participants will start a blinded treatment period of up to 24 weeks followed by an open label period of 28 weeks during which all participants will receive rilzabrutinib, and then a 4-week safety follow-up period or LTE.

At the end of 12 weeks of treatment, participants will be assessed for achieving a platelet response defined as a) platelet count of $\geq 50,000/\mu\text{L}$ OR a platelet count of between $\geq 30,000/\mu\text{L}$ and $<50,000/\mu\text{L}$ and at least doubled from baseline at any time during the first 12 weeks and b) absence of rescue medication in the 4 weeks prior to the elevated platelet count that meets platelet response criteria.

Figure 1 depicts the decision process for assessing response. The baseline value of platelet count is defined as the average of all the participant's Predose platelet counts (Screening and Study Day 1).

- Participants who respond will continue the blinded treatment period for a total of 24 weeks before entering the open label period.
- Participants who do not respond (including participants who receive rescue medication after 8 weeks of treatment) may discontinue from the study or enter the 28-week open label period at the end of Week 12, receiving treatment with 400 mg BID of rilzabrutinib. The Initial study medication assignment will remain blinded.

Figure 1 - Decision tree for assessing response at Week 13

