**Table 4 - Missing Data Handling for Primary Efficacy Endpoint**

Definition	Analysis Type	Estimand	Alternatives to main analysis	Missing data Handling	Missing data Assumption
Definition 1 a	Main c (Section 3.2.2)	Primary estimand (Composite)		No imputation of missing data	Not applicable
	Sensitivity (Section 3.2.3.1.3)		Alternative handling of missing data	Tipping-point analysis: post-treatment data considered missing for Intercurrent Event #3	Missing not at random: Assuming various treatment difference for missing data
	Sensitivity (for completers) (Section 3.2.3.2)	Modified primary estimand	Alternative analysis population	No imputation of missing data	Missing completely at random: completers are representatives of non-completers
	Sensitivity (Section 3.2.3.3)		Alternative handling of missing data due to Covid-19	Missing data due to Covid-19 imputed with the median value of available platelet counts	Missing (due to Covid-19) at random: missing data not associated with outcome
Definition 2 b	Main c (Section 3.2.2)	Primary estimand (Composite)		1) Missing data due to Covid-19 imputed with the median value of available platelet counts, 2) No response otherwise	1) Missing (due to Covid-19) at random: missing data not associated with outcome; 2) Missing (not due to Covid-19) not at random: Missing data indicates lack of response
	Sensitivity (Section 3.2.3.1.1)		Alternative handling of missing data	Missing data considered as no response	Missing not at random: Missing data indicates lack of response
	Sensitivity (Section 3.2.3.1.2)		Alternative handling of missing data	On-treatment missing data handled using multiple imputation	Missing at random: on-treatment missing data not associated with outcome
	Sensitivity (Section 3.2.3.1.3)		Alternative handling of missing data	Tipping-point analysis: post-treatment data considered missing for Intercurrent Event #3	Missing not at random: Assuming various treatment differences for missing data

Definition	Analysis Type	Estimand	Alternatives to main analysis	Missing data Handling	Missing data Assumption
	Sensitivity (for completers) ( Section 3.2.3.2 )	Modified primary estimand	Alternative analysis population	No imputation of missing data	Missing completely at random: completers are representatives of non-completers

All efficacy analyses based on ITT, unless otherwise specified.

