2. There are missing data that will need to be handled by multiple imputation in the placebo group and there are  $\geq 3$  participants in the placebo group who have completed the 24-week double-blind treatment without being rescued (after 8 weeks of double-blind treatment) and had post-baseline weekly platelet counts during the last 12 weeks of double-blind on-treatment period.

Please see sample SAS® code in [Section 5.7](#).

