## 4 SAMPLE SIZE DETERMINATION

A sample size of approximately 194 (129 versus 65 adult participants in the rilzabrutinib versus placebo arms, respectively) will provide 95% power to detect a 20% difference in response rates as defined in the primary endpoint ([Section 1.2.2.1](#)) between the 2 arms (25% vs 5%, in the rilzabrutinib versus placebo arms, respectively), using the Fisher's Exact test with a 0.05 two-sided significance level.

The assumption of a 25% response rate in the rilzabrutinib group is based on the Phase 2 study PRN1008-010 Part A (DFI17124 Part A) (durable response [8 out of the last 12 weeks with platelet count at or above 50,000/ $\mu$ L in the absence of rescue medication]) and the 5% response rate is estimated based on the observed placebo response in previous randomized controlled trials of ITP medications ([11](#)). The participants who are not evaluable for primary efficacy due to dropout or missing data will be considered as non-responders.

The pediatric sample size of 30 participants (20 participants on rilzabrutinib and 10 on placebo) was determined based on clinical practice and is adequate to descriptively describe the safety and efficacy in pediatric participants. With a sample size of 20 pediatric participants on rilzabrutinib the maximum width of an exact 90% CI on response rate would be 40%.

Calculations were made based on 2-sample Exact test using SAS® 9.4.

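### The 24-week completer analysis of the primary endpoint assumes completers represent non-completers, but the Week 13 rule and the rescue exclusion select completers on outcome, so it does not test robustness to dropout

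*SAP*

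**What the plan says.** SAP 3.2.3.2 plans sensitivity analyses in modified populations for both definitions of durable response. One of them assesses "The premature discontinuation by including participants who have completed the 24-week double-blind treatment period without rescue medication (ie, 24-week completer"). It uses the method of the main analysis (SAP 3.2.2). The section adds that the treatment difference will probably be estimated without stratification, because heavy dropout is expected, above all on placebo. Table 4 gives the assumption behind it as "Missing completely at random: completers are representatives of non-completers".

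Protocol Section 4 sets out who can become a completer. Platelet response is assessed at the end of 12 weeks: "Participants who respond will continue the blinded treatment period for a total of 24 weeks before entering the open label period". Those who do not respond, including those rescued after 8 weeks of treatment, either leave the study or enter open label. Footnote b to the Table 1 schedule of assessments gives non-responders the same two options.

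Protocol 10.3.9 counts participants who do not respond in the first 12 weeks and enter open label as non-responders. SAP 3.2.1 and 3.2.2 do the same for rescue after 8 weeks and for stopping because of lack of response or a related adverse event.

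**The concern.** Missing completely at random would require that finishing the blinded period has nothing to do with outcome. Here the protocol decides who finishes, and it decides on platelet counts and rescue. Both are measured after randomization, both can be affected by treatment, and both are tied to the endpoint. The completer comparison is therefore not a randomized one.

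Nor do the main reasons for exclusion create missing data. Week 13 non-response, lack of response, related adverse events and rescue after Week 8 are already scored as failures in the primary estimand. Removing those participants tests no missing-data assumption. It changes the question to how durable response is among people who have already shown an early one.

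What is at stake is interpretation. A smaller, null or reversed completer difference could be read as fragility of the primary result, and a larger one as confirmation. Neither reading would follow.

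**Working it through.** **The plan's own figure.** SAP Section 4 says 129 versus 65 adults "will provide 95% power to detect a 20% difference in response rates", for "25% vs 5%, in the rilzabrutinib versus placebo arms, respectively", by Fisher's exact test at two-sided 0.05. Enumerating the test over both binomial distributions gives 96.4%, and a normal approximation gives 96.5%. The stated 95% is reproduced to within 2 points.

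**Passages side by side.**
- Table 4: completers stand for non-completers.
- Protocol Section 4: the decision to stay blinded after Week 12 rests on a platelet criterion and on rescue.
- SAP 3.2.3.2: rescued participants are also left out, with no time limit stated. SAP 3.2.1 disqualifies only those rescued after 8 weeks. A participant rescued earlier could therefore be a durable responder in the main analysis and still fall outside the completer set.

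**Illustration of size.** The documents give no completion shares, so these are assumptions: c1 for rilzabrutinib and c0 for placebo. As a simplification, every durable responder is taken to complete unrescued. Then

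completer rate = ITT rate ÷ completion share, that is 25%/c1 and 5%/c0.

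Example: c1 = 60% and c0 = 30% give 25/0.60 = 41.7% and 5/0.30 = 16.7%, a difference of 25.0 points on about 77 and 20 participants.

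Completer difference in points, when the true ITT difference is 20 throughout:

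| c1 (completer rate) | c0 = 10% (50.0%) | c0 = 15% (33.3%) | c0 = 20% (25.0%) | c0 = 30% (16.7%) |
|---|---|---|---|---|
| 50% (50.0%) | 0.0 | +16.7 | +25.0 | +33.3 |
| 60% (41.7%) | −8.3 | +8.3 | +16.7 | +25.0 |
| 70% (35.7%) | −14.3 | +2.4 | +10.7 | +19.0 |

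The sign changes when 25/c1 = 5/c0, that is at c0 = c1/5. That is 10% placebo completion for c1 = 50% and 14% for c1 = 70%. At c0 = 10% there are only about 6 placebo completers (65 × 0.10 = 6.5). At every tabulated value of 15% or more the difference is positive.

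Had completion been unrelated to outcome, the completer rates would have stayed at 25% and 5% and the difference at 20 points, whatever the shares. The spread in the table comes entirely from selection.

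Fisher power over the same grid is about 3% to 76%. Little weight should be put on that, because the analysis has no decision rule and Fisher's test is not its planned method.

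**The case against.** The strongest reply is that nothing depends on this analysis. The decision rests on the stratified CMH test in the adult ITT population (SAP 3.2.2) and the fixed testing sequence (SAP 3.5). The completer analysis is labelled a modified estimand in an alternative population, and the SAP discloses the unequal dropout that it expects.

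Dropout is also examined elsewhere. The tipping-point analysis (SAP 3.2.3.1.3) keeps the adult ITT set for both definitions and varies the response rate among undetermined participants from 0% to 100% in each arm independently. For Definition 2, multiple imputation (SAP 3.2.3.1.2) covers unavailable counts in participants who stayed on treatment beyond Week 13, and SAP 3.2.3.1.1 counts all missing weeks as no response. All of this stands. It limits the consequence of the problem but does not make the Table 4 assumption true.

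Several stronger readings are tempting, and the documents do not support them:
- *Completers are selected on the endpoint itself.* The Week 13 criterion is one qualifying count at any time in 12 weeks, and a count of at least 30,000/µL will do if doubled from baseline. Completers can still fail the durable endpoint.
- *Most excluded participants have known outcomes.* Most of the exclusion categories do, but no split of numbers is given.
- *The SAP forecasts fewer than 3 placebo completers.* The condition in SAP 3.2.3.1.2 that mentions 3 placebo completers concerns only whether the Definition 2 multiple imputation is feasible.
- *The completer result will be null or reversed.* That depends on assumed shares and occurs only near 10% placebo completion.

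**Conclusion.** The stated assumption and the stated purpose of the completer analysis are wrong as written, for both definitions. This follows from the protocol's Week 13 rule and the rescue exclusion and needs no numerical assumption. The analysis describes durability among participants who met the Week 13 criterion and completed unrescued. Agreement or disagreement with the ITT result says nothing reliable about robustness to dropout.

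The −14 to +33 point range is illustrative. It rests on the planning rates of 25% and 5%, on assumed completion shares, and on all durable responders completing unrescued. That last condition is not exact. A Definition 1 responder could stop late for another reason once enough counts are in, and a participant rescued in the first 8 weeks may be excluded despite responding.

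A reader might infer that the primary result is unreliable or that the plan lacks a valid dropout check. Neither holds. The primary ITT analysis is unaffected, and the ITT sensitivity analyses address other-reason discontinuation. The correction is worth making so that an invalid comparison is not reported as a check on the pivotal endpoint.

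**What to change.** In SAP Table 4 (both definitions) and 3.2.3.2:
1. Remove the missing-completely-at-random assumption and the premature-discontinuation purpose for the completer set.
2. Present the set as a descriptive summary by arm among Week 13 responders who completed without rescue, with no p-value and not as a sensitivity analysis of the primary comparison.
3. State that robustness to dropout rests on the ITT tipping-point analysis (both definitions) and multiple imputation (Definition 2).

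If an exclusion analysis under a completely-at-random assumption is still wanted, exclude only adults whose status is undetermined in Table 5. Keep every determined responder and non-responder and use the same stratified CMH test. Say explicitly that Week 13 non-responders are kept as non-responders, because Table 5 has no separate row for them. Excluding everyone who stopped for other reasons would go too far, since it would delete participants whose status is already determined, including observed Definition 1 responders.

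The cost is SAP wording and, for the optional analysis, one population flag. No new data are needed. The downside is losing a conventional comparative completer table.

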### **3.2.3.3 Sensitivity Analyses – modified primary estimand – missing due to Covid-19 imputed with participant's median value (for Definition 1)**

Sensitivity analysis on the durable response Definition 1 will be carried out via the same primary estimand and the same analysis method as defined in the main analytical approach ([Section 3.2.2](#)), after the handling of missing data due to Covid-19. That is, missing data due to Covid-19 (per eCRF) will be imputed using the participant's median value of available weekly platelet counts (a minimum of 3 available weekly platelet counts required) during the last 12 weeks of double-blind on-treatment period.

### **3.2.4 Subgroup analyses**

To assess the homogeneity of the treatment effect across various subgroups, analyses will be performed on the primary endpoint (Definition 1 and Definition 2 respectively) in the adult ITT population across the following subgroups (categories with fewer than 5 participants may be combined with other categories):

- Race (White, Asian, Other)
- Age group (<65 years, ≥65 years)
- Sex (Male, Female)
- Duration of ITP since diagnosis (≤1 year, >1 year to ≤3 years, >3 years)
- Prior splenectomy status (yes, no)
- Baseline platelet counts (<15,000/μL, ≥15,000/μL)
- Prior CS (No prior CS, Prior CS and no concomitant CS, Prior and concomitant CS, Prior CS and concomitant CS and TPO-RA)
- Prior TPO-RA (No prior TPO-RA, Prior TPO-RA and no concomitant TPO-RA, Prior and concomitant TPO-RA, Prior TPO-RA and concomitant TOP-RA and CS)
- Prior intravenous immunoglobulin (IVIg) or anti-D immunoglobulin (Yes, No)
- Prior rituximab (Yes, No)
- Concomitant ITP medications (Yes, No)
- Concomitant ITP medications (CS, TPO-RA, both CS and TPO-RA, neither CS nor TPO-RA)
- US vs. Non-US
- Geographic region:
  - Asia/Pacific (Australia, China, Japan, Singapore, South Korea, Thailand),

- West Europe (Austria, France, Germany, Italy, Norway, Spain, United Kingdom, Netherlands),
- East Europe (Hungary, Israel, Poland, Russia, Turkey, Ukraine),
- North America (Canada, United States),
- South America (Argentina, Brazil, Chile, Mexico).

The observed response rate will be presented along with its associated 95% asymptotic CI in each treatment group and each subgroup. The treatment difference in response rates and its associated 95% CI will be summarized for the subgroups defined above. The treatment difference for each subgroup will likely be estimated via normal approximation without being adjusted by stratification factors due to the expected small cell size. The Mantel-Haenszel estimate of common treatment difference and associated 95% ([Section 3.2.2](#)) adjusted by stratification factors may be considered if appropriate. The analysis method and stratification factors will be specified in the footnote of the corresponding outputs. The consistency of the treatment difference among these sub-populations will be examined by the forest plot.

### 3.3 SECONDARY ENDPOINT(S) ANALYSIS

#### 3.3.1 Key/Confirmatory secondary endpoint(s)

##### 3.3.1.1 Definition of endpoint(s)

Please see [Section 1.2.2.2](#) for the definition of key secondary efficacy endpoints. Additional details are provided below for specific endpoints.

*Number of weeks with platelet count  $\geq 50,000/\mu\text{L}$  OR between  $\geq 30,000/\mu\text{L}$  and  $< 50,000/\mu\text{L}$  and at least doubled from baseline over the 24-week blinded treatment period in the absence of rescue therapy*

To qualify for having a platelet response at a given week, a participant must have met ALL the following criteria,

- Platelet count  $\geq 50,000/\mu\text{L}$  OR between  $\geq 30,000/\mu\text{L}$  and  $< 50,000/\mu\text{L}$  and doubled from baseline at a given week during the 24-week double-blind treatment period from Week 2 (Day 8) to Week 25 (Day 169) ([Section 3.2](#)),
- Not rescued within the 4 weeks prior to the elevated platelet count at the given week. If a participant receives rescue medication during the 24-week double-blind treatment, the participant's platelet counts will be censored from the date when the rescue medication is initiated up to 4 weeks after the use of rescue medication, i.e., any weeks that fall into this period will be considered to have had no platelet response.

*Number of weeks with platelet count  $\geq 30,000/\mu\text{L}$  and at least doubled from baseline over the 24-week blinded treatment period in the absence of rescue therapy*

Similar derivation will be applied as the secondary endpoint above.

*Time to first platelet count of  $\geq 50,000/\mu\text{L}$  OR between  $\geq 30,000/\mu\text{L}$  and  $< 50,000/\mu\text{L}$  and doubled from baseline (platelet counts will be censored for 4 weeks after the use of rescue therapy, if any)*

Time to first platelet count in days will be calculated as:

$$(\text{Date of first occurrence of platelet response} - \text{Date of first IMP dosing}) + 1,$$

where platelet response is defined as  $\geq 50,000/\mu\text{L}$  OR between  $\geq 30,000/\mu\text{L}$  and  $< 50,000/\mu\text{L}$  and doubled from baseline. Please see the censoring rule, handling of intercurrent events and missing data in [Section 3.3.1.2.2](#) and [Section 3.3.1.3.1](#).

*Proportion of participants requiring rescue therapy during the 24-week Blinded Treatment period*

Participants requiring rescued therapy are those who are rescued after first double-blinded IMP administration and before Week 25 or last double-blinded IMP administration, whichever earlier. The Kaplan-Meier (K-M) method will be used to estimate the probabilities of first rescue therapy use. Please see handling of intercurrent events and the censoring rule in [Section 3.3.1.2.3](#).

*Change from baseline in Item 10 of ITP-PAQ at Week 25; Change from baseline in IBLIS assessment at Week 13*

Please refer to [Section 3.7.3](#).

